4.2 PARTICIPANT EXCLUSION CRITERIA

An individual who meets any of the following criteria will be excluded from participation in this study:

1. Malignant disease, other than that being treated in this study, with exception of non-metastatic prostate cancer, treated Stage I breast cancer, skin malignancies.
2. Implanted pacemaker, defibrillator or deep brain stimulator, or documented clinically significant arrhythmias.
3. Active implanted medical device (e.g. deep brain stimulators, spinal cord stimulators, vagus nerve stimulators, pacemakers, defibrillators, and programmable shunts).
 - a. External medical devices (e.g., insulin pumps) are permitted.
4. Skull defect (e.g. missing bone with no replacement).
5. Shunt.
6. Bullet fragments
7. Evidence of increased intracranial pressure (midline shift > 5 mm, clinically significant papilledema, vomiting and nausea or reduced level of consciousness).
8. Sensitivity to conductive hydrogels.

9. Pregnant or lactating women.
10. Underlying serious skin condition on the scalp, which in the opinion of the investigator, would prevent or interfere with TTField therapy.
11. Any condition that, in the opinion of the investigator, would interfere with evaluation of study treatment or interpretation of participant safety or study results.

4.3 STRATEGIES FOR RECRUITMENT AND RETENTION

Participants for this study will primarily be recruited from Hematology/Oncology or Radiation Oncology practices within either OHSU, UW Seattle, Mayo Clinic Arizona or Ohio State University. Participants may be identified and referred to this study by their primary treating physician from within OHSU, UW Seattle, Mayo Clinic Arizona, Ohio State University or from the outside community. Participants may also initiate contact with the investigator through information of this study posted on the clinicaltrials.gov website. This pilot study aims to enroll 106 participants, approximately half from each investigational study site. Total time to accrual will be approximately 24 months.

ACCRUAL ESTIMATES

A total of 106 participants anticipated to be equally enrolled from the four participating study sites, OHSU, UW Seattle, Mayo Clinic Arizona, and Ohio State University. Among these 106 participants, we expect to enroll 45 patients with extensive stage disease and 61 patients with limited stage disease. We will continue enrolling patients from the four sites until the targeted sample size has been reached within each disease category (i.e. we will stop enroll patients with extensive stage disease if the number has reached 45, but will continue to enroll subjects with limited stage disease until we have 61 patients in the sub-category, and vice versa.) .

No OHSU Knight Cancer Institute study will focus on any particular gender, racial or ethnic subset. No participant will be excluded from the study on the basis of gender, racial or ethnic origin. Male, female and minority volunteers will be recruited for this study from the general population and approximately 50% men and 50% women will be studied. Gender-nonconforming and gender-fluid individuals as members of the general population will also be recruited.

The projected gender, racial, and ethnic composition of the study will represent that of the states of Oregon (**Table 1**), Washington (**Table 2**), Arizona (**Table 3**), and Ohio (**Table 4**).

4.3.2 Medicare Coverage Related to Investigational Device Exemption (IDE) Studies

In this study Medicare beneficiaries will be given access to potentially useful therapies available in the clinical trial context. Enrollment of Medicare beneficiaries in clinical trials will allow collection of sufficient evidence to demonstrate or not demonstrate a new therapy's effectiveness for use in the Medicare population based on age, disability, or other eligibility status. The Medicare Prescription Drug, Improvement, and Modernization Act of 2003 (MMA) allowed Medicare payment of the routine costs of care furnished to Medicare beneficiaries in certain categories of Investigational Device Exemption (IDE) studies. Covering the costs in these IDE studies removes a financial barrier that could otherwise discourage Medicare beneficiaries from participating. CMS finalized changes to the IDE regulations (42 CFR § 405 Subpart B), effective January 1, 2015. CMS added criteria for coverage of IDE studies and changed from local Medicare Administrative Contractor (MAC) review and approval of IDE studies to a centralized review and approval of IDE studies.

An approval for a Category A (Experimental) IDE study will allow coverage of routine care items and services furnished in the study, but not of the Category A device, which is statutorily excluded from coverage.

Table 1. Projected accrual for present study based on Oregon population demographics

	Females		Males		Totals	
	N	% OR pop.	N	% OR pop.	N	% OR pop.
Ethnic category						
Hispanic or Latino	2	6.6	3	6.5	5	13.1
Not Hispanic or Latino	12	43.8	10	37.9	22	86.9
Ethnic category participant totals*	14		13		27	100*
Racial category						
American Indian or Alaskan Native	0-1	0.9	0-1	0.9	1	1.8
Asian	1	2.4	1	2.3	2	4.7
Black or African American	0-1	1.1	0-1	1.0	1	2.2
Native Hawaiian or other Pacific Islander	0	0.2	0	0.2	0	0.4
White	10	43.9	9	43.2	21	87.1
Two or more races	1	1.9	1	1.9	2	3.8
Racial category participant totals*	14	50.4	13	49.6	27	100

Source: Adapted from U.S. Census Bureau, 2017.

N, projected participant accrual based on percentage of OR population demographic (% OR pop.).

*Totals may not equal 100 due to rounding.

Table 2. Projected accrual for present study based on Washington population demographics

	Females		Males		Totals	
	N	% WA pop.	N	% WA pop.	N	% WA pop.
Ethnic category						
Hispanic or Latino	3-4	6.4	3-4	6.4	7	12.7
Not Hispanic or Latino	10	43.7	9	43.7	20	87.6
Ethnic category participant totals*	14		13		27	100*
Racial category						
American Indian or Alaskan Native	1	1.0	1	1	1	1.9
Asian	2-3	4.5	2-3	4.5	5	8.9
Black or African American	1	2.1	1	2.1	2	4.2
Native Hawaiian or other Pacific Islander	0	0.4	0	0.4	0	0.8
White	9	39.8	9	39.8	18	79.5
Two or more races	1	2.4	1	2.3	2	4.6
Racial category participant totals*	14	50.0	13	50.0	27	100

Source: Adapted from U.S. Census Bureau, 2017.

N, projected participant accrual based on percentage of WA population demographic (% WA pop.).

*Totals may not equal 100 due to rounding.

Table 3. Projected accrual for present study based on Arizona population demographics

	Females		Males		Totals	
	N	% AZ pop.	N	% AZ pop.	N	% AZ pop.
Ethnic category						
Hispanic or Latino	3	15.5	3	15.5	6	31.1

Not Hispanic or Latino	10	43.7	10	43.7	20	54.1
Ethnic category participant totals*	13		13		26	100*
Racial category						
American Indian or Alaskan Native	1	2.5	1	2.5	1	5.3
Asian	2-3	1.6	2-3	1.6	5	3.2
Black or African American	1	2.1	1	2.1	2	5.2
Native Hawaiian or other Pacific Islander	0	0.	0	0.4	0	0.3
White	8	41.3	8	41.3	16	82.6
Two or more races	1	1.4	1	1.4	2	2.9
Racial category participant totals*	13	50.0	13	50.0	26	100

Source: Adapted from U.S. Census Bureau, 2017.

N, projected participant accrual based on percentage of AZ population demographic (% AZ pop.).

*Totals may not equal 100 due to rounding.

Table 4. Projected accrual for present study based on Ohio population demographics

	Females		Males		Totals	
	N	% OH pop.	N	% OH pop.	N	% OH pop.
Ethnic category						
Hispanic or Latino	3	6.0	3	6.0	6	14.0
Not Hispanic or Latino	10	44.7	10	44.7	20	78.4
Ethnic category participant totals*	13		13		26	100*
Racial category						
American Indian or Alaskan Native	1	1.0	1	1	1	0.3
Asian	1-2	1.2	1-2	1	1	2.5
Black or African American	2-3	6.5	2-3	6.5	4	13.1
Native Hawaiian or other Pacific Islander	0	0.05	0	0.05	0	0.1
White	8	40.5	8	40.5	20	81.1
Two or more races	1	1.2	1	1.2	2	2.4
Racial category participant totals*	13	51.0	13	49.0	26	100

Source: Adapted from U.S. Census Bureau, 2017.

N, projected participant accrual based on percentage of OH population demographic (% OH pop.).

*Totals may not equal 100 due to rounding.

4.3.3 INCLUSION OF CHILDREN

This protocol does not include children (<18-years-old) as the number of children with SCLC is limited.

4.4 REGISTRATION PROCEDURES

In order to participate in this study signed informed consent will be obtained from the participant. The Institutional Review Board (IRB) approved informed consent must be signed and dated by each participant prior to undergoing any study procedures or before any prohibited medications are withheld from the participant in order to participate in this study.

PARTICIPANT REGISTRATION

4.4.1.1 Local Registration

This is a single-arm phase II trial, and there is no randomization for treatment.

Participants will be required to give written informed consent to participate in the study before any screening tests or evaluations are conducted that are not part of standard care.

Registration from all consented participants must be entered into the OHSU electronic Clinical Research Management System (CRMS, e.g., eCRIS). At a minimum, registration of OHSU participants will include: Signed copies of the most recently IRB-approved, informed consent form and HIPAA authorization

4.4.1.2 Multicenter Registration

The OHSU coordinating center study team manages the participant registration process. Investigators at participating sites identify eligible participants and send source documents that support eligibility to OHSU for review and verification before the participating site may enroll and treat the participant. The OHSU coordinating center team verifies completeness of documents, enters registration information into the Knight CRMS, and assigns a study number/identifier. The coordinating center sends an email to the participating site indicating whether or not the participant is eligible and assigns a participant number/identifier.

Registration will include a minimum of the following:

- De-identified source documentation of eligibility
- Signed copies of the most recently IRB-approved, informed consent form and HIPAA authorization.

Each site is expected to maintain a screening log of all participants who are approached for the study. The log documents an explanation for exclusion due to screen failure. This log should be submitted to the coordinating center on a regular basis. Participating sites are required to retain, in a confidential manner, sufficient information on each participant so that the participant may be contacted should the need arise.

4.5 PARTICIPANT SCREENING AND ENROLLMENT

In order to participate in this study, signed informed consent must be obtained from the participant or the participant's legally acceptable representative. The current Institutional Review Board (IRB) approved informed consent must be signed and dated by each participant prior to undergoing any study procedures or before any prohibited medications are withheld from the participant in order to participate in this study.

Screening will begin once the participant has provided written informed consent to participate in the study and ends on Day 1 of the study. All screening and baseline evaluations will be performed during the screening phase (i.e., up to 10 days before initiating TTField therapy). Day 1 of the clinical trial will be when participants start TTField therapy. Total accrual of all participants is anticipated to take a total of 24 months.

4.6 PARTICIPANT WITHDRAWAL OR DISCONTINUATION

Participants are free to withdraw consent and discontinue participation in the study at any time and without prejudice to further treatment. If a participant no longer wants to receive investigational product, but is willing to come for follow-up appointments, the participant's

request should be honored, if possible. The following are examples demonstrating why a participant's treatment might be discontinued:

- Toxicity precludes further study treatment.
- There is a need for any treatment not allowed by the protocol.
- The participant fails to meet the criteria for study treatment.
- Disease recurrence or progression.
 - TTFields therapy has been established to control supratentorial primary glioblastoma. TTFields may control supratentorial disease better than infratentorial disease. Participants that develop supratentorial metastatic lesions will be removed from the study. Participants that develop infratentorial metastases, or systemic metastases, will be able to continue with treatment for the duration of the 12 months treatment period.
- Investigator's discretion.

No further participant contact should be made if the participant withdraws consent for participation in the study. Information about the reason(s) for discontinuation and collection of any new or ongoing adverse events (AEs) should be collected at the time the participant withdraws consent.

For all other reasons for discontinuation from the study treatment phase, the participant should return to the clinic for the end of treatment (EOT) visit according to Section 7.

HANDLING PARTICIPANT WITHDRAWAL AND DISCONTINUATION

Participants that withdraw or discontinue from this study will not be replaced.

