Secondary Objectives	1. Rate of brain metastases following TTField therapy at 12 months. 2. Overall survival of participants with SCLC after using TTField therapy. 3. TTField therapy related side-effects. 4. Quality of life among participants using TTField therapy. 5. Observed rate of brain metastases 6-month from the beginning of the 4 th cycle of chemotherapy to development of brain metastases
Primary Endpoints	Incidence of SCLC brain metastases at 6 months from the start of TTField therapy
Secondary Endpoints	1. Incidence of SCLC brain metastases at 12 months 2. Overall survival 3. Incidence of TTfield related adverse events 4. Quality of life 5. Incidence of SCLC brain metastases at 6 month from the beginning of the 4 th cycle of chemotherapy to development of brain metastases

	metastases
Number of Participants	A total of 106 participants will be enrolled in this study. Among these, target enrollment will include 45 participants with extensive stage disease, and 61 participants will have limited stage disease.
Duration of Therapy	Participants will receive TTField therapy for 12 months, or until development of brain metastases, whichever comes first.
Duration of Follow Up	Participant followed up will continue until death.
Inclusion Criteria	
 • ≥ 22 years of age • Biopsy-proven SCLC • Clinical Response to standard of care chemo- and/or radiotherapy, as defined by no thoracoabdominal tumor progression on CT imaging within 12 weeks prior to enrollment. • No contraindications to treatment with Optune®. • No other active malignancies, with exception of non-metastatic prostate cancer, treated Stage I breast cancer, skin malignancies • No brain metastases [gadolinium MRI < 12 weeks before enrollment]. • No mental conditions that would prevent compliance. • Life expectancy of at least 3 months. • ECOG ≤ 2.
Exclusion Criteria	
 • Progressive disease. • Pregnant • Implanted pacemaker, programmable shunts, defibrillator, deep brain stimulator, other implanted electronic devices in the brain, or documented clinically significant arrhythmias. • Evidence of increased intracranial pressure (midline shift > 5mm, clinically significant papilledema, vomiting and nausea or reduced level of consciousness)

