Participants with either LS-SCLC or ES-SCLC must be no more than 6 weeks from having received last dose of chemotherapy for primary tumor (per institutional guidelines), and must have at least demonstrated a partial response to treatment, to be considered eligible for TTField therapy with the Optune® device. Participants are encouraged to undergo TTField therapy (200 kHz) for a minimum of 18 hours per day for a period of 12 months, or until the confirmed appearance of metastatic brain lesions, whichever comes first. Participants that develop numerous (>10) supratentorial metastatic lesions before 12 months will discontinue further use of TTFields and will receive palliative/supportive care per institutional guidelines (e.g., whole brain radiotherapy). Participants that develop either limited (≤ 10) supratentorial or any number of infratentorial metastases will remain eligible to continue with TTFields therapy for the duration of the 12 months after the brain metastatic lesions are addressed according to institutional guidelines (e.g. partial brain irradiation stereotactic radiosurgery, stereotactic body radiation therapy). Systemic progression will be managed per institutional guidelines (e.g. systemic chemotherapy, immunotherapy, radiation therapy, etc.) and patients will remain eligible to continue with TTFields therapy for the duration of the 12 months. While on-study, participants will be clinically evaluated every 2-3 months per NCCN guidelines and will all be monitored remotely by phone calls monthly and will undergo gadolinium (gd)-MRI of the head at 6 months to assess occurrence of disease progression (per RECIST v1.1). Participants will be subject to periodically answering quality of life (QoL) questionnaires (i.e., baseline, 6 and 12 months after initiating treatment). At the end of study, participants will undergo clinical follow-up 1 and 3 months after completion of TTField therapy. Subsequent follow-up until death (up to 5 years) will be in accordance with standard of care (i.e., every 3 months during years 1 and 2 following last chemo-radiotherapy, then every 6 months thereafter).

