4.7 OFF-STUDY CRITERIA

Criteria that can take a participant off-study include:

- Participant requests to be withdrawn from study without further follow-up,
- Completed study follow-up period,
- Death,
- Screen failure

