6.3 TREATMENT PERIOD AND MAINTENANCE

Participants will receive TTField therapy on continuous basis (i.e., 18-24 hours a day, 7 days a week) for a period of 12 months. Participants that develop supratentorial metastatic lesions (>10) before 12 months will discontinue further use of TTFields and will be provided supportive/palliative treatments and supportive care (e.g., management of radionecrosis) consistent with institutional standard of care (e.g., whole brain radiation therapy). Participants that develop either limited (≤ 10) supratentorial or any number of infratentorial metastases will remain eligible to continue with TTFields therapy for the duration of the 12 months after the brain metastatic lesions are addressed according to the institutional guidelines (e.g. partial brain irradiation, stereotactic radiosurgery, stereotactic body radiation therapy). These participants will be clinically monitored per institutional guidelines. Participants that develop systemic progression, which can be treated per institutional standard of care (e.g. systemic chemotherapy, immunotherapy, radiation therapy, etc.), may remain eligible to continue with TTField therapy for the duration of the 12 months treatment period. Information regarding systemic therapy must be recorded in CRF.

After 12 months study period, participants will not be able to stay on the TTField therapy, and will be clinically monitored per institutional guidelines.

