6.6 PROHIBITED MEDICATIONS, TREATMENTS, AND PROCEDURES

Participants can receive anti-cancer systemic chemotherapy, biological therapy, immunotherapy, or radiation therapy while receiving TTField therapy per standard of care or the clinical discretion of the investigator. Participants that have disease progression requiring clinical intervention with one or more of the aforementioned treatments can remain on the study as long as there is no widespread supratentorial disease progression (>10 lesions). Participants may receive other medications that the investigator deems to be medically necessary.

Participant exclusion criteria (Section 4.2) describes other medications prohibited in this trial.

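### The protocol gives incompatible rules for a participant who develops a brain metastasis, so device exposure, and possibly follow-up, after the primary event depends on which section a site follows

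*Combined protocol and SAP*

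**What the plan says.** The following places in the current text govern what happens when disease appears in the brain, and they do not agree.

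- **Synopsis, Duration of Therapy:** "Participants will receive TTField therapy for 12 months, or until development of brain metastases, whichever comes first". Neither lesion site nor lesion count qualifies this. The sentence on treatment duration in section 3.1 has the same effect once brain lesions are confirmed.
- **Section 3.1, further on:** "Participants that develop numerous (>10) supratentorial metastatic lesions before 12 months will discontinue further use of TTFields". By contrast, "Participants that develop either limited (≤ 10) supratentorial or any number of infratentorial metastases will remain eligible to continue with TTFields therapy" once the lesions have been managed locally. Section 6.3 repeats this split.
- **Section 4.6:** "Participants that develop supratentorial metastatic lesions will be removed from the study". It then says "Participants that develop infratentorial metastases, or systemic metastases, will be able to continue with treatment for the duration of the 12 months treatment period".
- **Section 6.6:** participants whose progression needs treatment "can remain on the study as long as there is no widespread supratentorial disease progression (>10 lesions").
- **Section 6.1 and the Figure 1 text:** treatment lasts 12 months or to disease progression, whichever is earlier. Sections 3.1, 4.6 and 6.3 nevertheless allow the device to continue after systemic progression.

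On follow-up, section 7.6 and footnote J of the schedule of events commit to survival status for every participant after the device is stopped, and the Synopsis plans follow-up to death. Section 4.7, which opens "Criteria that can take a participant off-study include", lists withdrawal without further follow-up, completed follow-up, death and screen failure. Brain metastasis is not on that list.

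**The concern.** The event that triggers the conflict is the primary endpoint event, so this is not a rare case at the edge of the protocol. A participant with a single supratentorial lesion leaves the study under 4.6, stops the device under the Synopsis, and may go on using it under 6.3. Four sites enroll, and no section is said to take precedence.

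The primary event has happened by then, but much of the secondary information has not been collected. The plan still intends to report overall survival to 60 months, device-related adverse events to 12 months, and quality of life and MMSE at 6 and 12 months. Section 10.2 also names device compliance as an example covariate in the model that looks for differences between centers. If sites follow different sections, exposure after the event could become entangled with center, which is the factor that model examines.

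**Working it through.** **Step 1. The rules side by side.**

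| Source | 1 to 10 supratentorial lesions | More than 10 supratentorial | Infratentorial only | Systemic progression only |
|---|---|---|---|---|
| Synopsis; duration sentence of 3.1 | device ends | device ends | device ends | not a stopping event |
| 6.1; Figure 1 text | device ends | device ends | device ends | device ends |
| Later sentences of 3.1; 6.3 | may continue | device ends | may continue | may continue |
| 4.6 | leaves the study | leaves the study | may continue | may continue |
| 6.6 | may stay on the study | by implication, may not stay | may stay | may stay |

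Only the second case gets a consistent answer about the device. Even there the text differs on whether the participant stops the device or leaves the study. Section 3.1 contradicts itself in the first and third cases.

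**Step 2. The plan's own figures.** Section 10.3 tests 40% against 20% in extensive stage (ES) and 30% against 15% in limited stage (LS), with a two-sided exact test at 5% and 80% power. With at most 2.5% in each tail:

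- ES: the smallest n is 45. Reject at 11 or fewer, or 26 or more, events. Attained alpha is 0.034 and power 0.826.
- LS: the smallest n is 61. Reject at 11 or fewer, or 26 or more, events. Attained alpha is 0.049 and power 0.804.

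Both sample sizes reproduce. Nothing in Step 1 alters them, because the first metastasis counts as the event under every rule.

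**Step 3. How many participants reach the conflict by month 6.** Expected count = n × rate.

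- At the targeted rates: 45 × 0.20 + 61 × 0.15 = 9.0 + 9.15 = 18.15, or 17% of 106.
- At the historical rates: 45 × 0.40 + 61 × 0.30 = 18.0 + 18.3 = 36.3, or 34% of 106.

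These are all brain metastases. Section 4.6 disagrees with 3.1, 6.3 and 6.6 on continuation only for participants with 1 to 10 supratentorial lesions. Call their share s. The documents do not give s, so it is taken over its whole range:

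| Assumed s | Targeted rates | Historical rates |
|---|---|---|
| 0% | 0 | 0 |
| 50% | 9 | 18 |
| 100% | 18 | 36 |

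The Synopsis conflict is wider, since it also covers participants with infratentorial lesions only.

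**Step 4. Which outputs can move.**

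- *6-month incidence tests:* unchanged.
- *Compliance covariate and center comparison:* section 10.2 does not say over what period compliance is measured. If the period runs past the event, the stopping rule a site follows enters the covariate.
- *Adverse events to 12 months:* both time on the device and time under observation could differ.
- *Quality of life and MMSE:* assessments could be moved or missed, and section 10.4 rules out imputation.
- *Overall survival:* affected through follow-up only if 4.6 is taken to end follow-up. Censoring would then occur at brain metastasis and would probably be informative.

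**The case against.** The strongest reply is that 4.6 does not mean what its wording suggests. The sentence sits in a list of examples of why treatment might stop. The same section sends participants who leave the treatment phase, other than by withdrawing consent, to an end-of-treatment visit. Section 7.6, footnote J and the Synopsis all keep survival follow-up going. Table 3 in section 7.1 equates the 12-month questionnaire with the end-of-treatment visit, so an assessment at discontinuation is plausible, although earlier than 12 months. Overall survival, quality of life and MMSE carry no hypothesis tests. The coordinating center also reviews source documents for compliance (section 12.5).

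Most of this stands, and it rules out two inferences a reader might draw. The first is that Kaplan-Meier survival is biased upward. The documents support that only for a site that follows 4.6 literally against 7.6, and they do not quantify how strongly brain metastasis predicts death. The second is that the 12-month quality-of-life and cognitive data are lost for these participants. A shift in timing is at least as likely.

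The reply does not settle everything. The continuing commitment in 7.6 to all participants after the device stops is to survival status, not to questionnaires or MMSE. Section 4.7 helps less than it seems to, because its list is introduced as what the criteria include and is not clearly exhaustive. Nothing in the reply touches the conflict over device exposure.

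**Conclusion.** The contradiction is real and lies in current operative text. It should be corrected, but it does not threaten the primary analysis. About 18 to 36 of 106 participants would have a brain metastasis by month 6, if the plan's targeted and historical rates bracket the truth. Between 0 and 36 of them would be handled differently by 4.6 than by 3.1, 6.3 and 6.6. The width of that range reflects the missing split by lesion site and number.

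Exposure after the event could differ by the section followed. Harm to the survival analysis is conditional on a literal reading of 4.6. A reader might also project these counts to 12 months at a constant hazard. The documents give no 12-month rate, and section 1.1 puts median survival in extensive stage at about 9 to 10 months from diagnosis, so death competes with the event and such a projection would probably be too high.

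**What to change.** Two separate changes are needed.

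1. Reconcile the Synopsis, the Figure 1 text and sections 3.1, 4.6, 6.1, 6.3 and 6.6 to a single device-stopping rule covering supratentorial, infratentorial and systemic progression. Which rule is a clinical decision for the sponsor, and nothing here favors one.
2. Make 4.6 distinguish stopping the device from leaving the study. State that, after the device is stopped and unless consent is withdrawn, survival follow-up continues as in 7.6 and the scheduled adverse-event, quality-of-life and MMSE assessments continue. Section 4.7 does not mention adverse events, and the collection windows in 7.1, footnote H and 9.5 differ (9.5 ends at alternative therapy), so the new text must say which window applies. Section 6.2 and the pregnancy text in 6.4 also speak of removal from the study and should be checked for the same ambiguity.

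The cost is amendment wording plus some continued assessments after the device is stopped. Survival follow-up is already planned. The sample size and the primary test do not change.
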